In Mpumalanga, Gert Sibande and Nkangala Districts have significant gaps to identifying people living with HIV (PLHIV) who are not on antiretroviral therapy (ART), and reaching their ART targets, especially in adult men. In line with prior research of HIV treatment, estimate that over 65% of PLHIV not on ART are men (1), which is a gap of ~39,000 men living with HIV needing to be tested and initiated on ART. To diagnose over 60,000 new PLHIV or PLHIV not on ART (38,000 in Gert Sibande and 30,000 in Nkangala) and initiate them on ART in the next year (PEPFAR, Implementing Partner data, August 2020), innovative testing strategies are required. Index partner testing, defined as testing partners of individuals living with HIV, has not been brought to scale in Mpumalanga, despite research demonstrating the positive impact of index testing.(10, 11) To improve case finding among men in these districts we propose to evaluate how best to reach partners of PLHIV (newly diagnosed or on ART) with index testing by using HIV self-screening (HIVSS) and linkage to ART start.

Secondary distribution of HIV self-screening kits (HIVSS), whereby clients bring HIVSS kits to their partners, addresses many important barriers by enabling sex partners to screen themselves at their convenience and in the privacy of their own homes (12). HIVSS is a particularly promising strategy to engage African men who are less likely to attend clinic services or receive clinic-based HIV testing (13). Male clients perceive HIVSS as a strategy that saves the time and cost spent going to a clinic for testing, reduces stigma, and prepares them for retesting or confirmatory testing in the clinic (14). Secondary HIVSS distribution dramatically increased male partner and couples testing in antenatal and postpartum care settings in Kenya (15), male partner testing in antenatal care settings Malawi (16), and male partner testing in Malawi among HIV-positive women accessing ART services (10). Few adverse events, including intimate partner violence (IPV), have been associated with secondary HIVSS distribution strategies in five randomized trials (12). However, several gaps remain.

- First, there is an urgent need to examine secondary distribution of HIVSS by women to male partners in **South Africa**. Few HIVSS studies have been conducted in South Africa which has very different epidemic and contextual factors (e.g., higher levels of IPV) versus Kenya and Malawi where most previous studies were conducted. In contrast to the higher acceptability of HIVSS reported by clients in Kenya and Malawi (17) some studies from South Africa indicate that acceptability may be low which could greatly limit HIVSS impact, while other studies indicate that acceptability may be high in South Africa (18). To our knowledge, no randomized controlled trials of the effectiveness of secondary HIVSS distribution have taken place among South Africa adults.
- Second, more research is needed to **validate partner HIVSS use and results** after distribution. A systematic review found that three strategies may be able to verify HIVSS results (supervision by a health provider, returning used kits, and electronic transmission of photographs), but evaluation and development of innovative strategies for verifying HIVSS use and results is urgently needed (19).

- Finally, prior trials of HIVSS have focused on primary outcomes of HIVSS uptake among partners. It is additionally and critically important to understand whether HIVSS strategies lead to **improved partner ART uptake** among newly diagnosed men.

COVID-19 and study implications. The Department of Health and PEPFAR partners, including BroadReach Healthcare, have continued to offer HIV testing, treatment and monitoring during the COVID-19 lockdown in South Africa as HIV services are essential health services. The team will continue to observe all Department of Health infection prevention and control methods. The proposed intervention is important during the COVID-19 lockdown as it is designed to promote HIV testing and case finding from home to improve linkage to treatment from the HIV+ partner.

3. Study Objectives:

We will partner with BroadReach Healthcare, a PEPFAR partner in South Africa, to pilot test an innovative index partner HIVSS strategy in one urban and one rural public health clinic in the Nkangala district of Mpumalanga Province to evaluate **acceptability, barriers, and preliminary efficacy** of secondary HIVSS distribution in a randomized control trial enrolling women newly diagnosed with HIV or on ART. In the intervention arm, women will receive counselling on how to use HIVSS, how to encourage their male partner to screen, and 2 HIVSSs with HIVSS instructions and invitation to return for confirmatory testing. In the standard of care arm, index women will receive counselling on the importance of disclosure to their family and partner(s) and referral for HIV testing (per SA national guidelines). We will evaluate the following aims:

1. Conduct a mixed-methods survey with N=100 HIV+ women to assess perceived **acceptability and barriers** (including perceived safety, IPV) to secondary HIVSS distribution by women to male partners.
2. Test the **feasibility** and **preliminary efficacy** of secondary HIVSS distribution through a 1:1 randomized control trial in n=100 HIV+ women to assess, comparing standard of care to intervention arm:
 - a. % of index women who self-report that they gave the HIVSS or standard of care referral for testing to their male partner
 - b. % of male partners who either screened or tested for HIV assessed at 3 months after randomization (*primary outcome*)
 - i. Measured via options of: index or partner self-report, SMS/WhatsApp of a picture of the used HIVSS sent by partner or index, return of a used self-test to the facility by either the index or partner, and/or partner coming into facility for with an invitation for confirmatory testing or SOC counseling referral
 - c. % of male partners with a positive HIV screening/test result
 - d. % of newly diagnosed male partners who initiate ART within 3 months of diagnosis
 - e. % of those on ART with viral suppression after 6 months on ART (index and partners)
3. In the intervention arm, we will assess acceptability and barriers (including safety/IPV) related to HIVSS distribution or use via surveys with all intervention participants who return for the study endline survey and a convenience samples of n=20 male partners (n=10 men who used HIVSS and n=10 men who did not use HIVSS)

We will publish these results to inform PEPFAR index and HIVSS implementation in South Africa. This study will inform a larger trial to apply for a large research grant to the US National Institute of Health (NIH) in late 2021.

3. Study design

Randomized control trial of n=100 WLHIV (50 in each arm) in two facilities in the Nkangala district. We selected high-density facilities, Kwamhlanga CHC and Sr Mashiteng Clinic facility from a rural and urban area, respectively, to ensure that the results are generalizable. These facilities use oral HIV test kits, which has been shown to be more acceptable in terms of ease of use (20, 21). WLHIV will be recruited in antenatal care or in HIV care services. Inclusion criteria are listed below.

Inclusion Criteria:

1. Adult female 18+ years old
2. confirmed HIV-positive or on ART
3. confirmed to currently have a male partner and are sexually active
4. male partner is of HIV- or unknown status
5. confirmed to have a cell phone that can read and respond to SMS/WhatsApp messages
6. confirmed to be able to consent to study participation (no language constraints or psychological issues that would make it difficult to consent to participate in the study)

Exclusion criteria: Failure to meet all of inclusion criteria

Procedures for the informed consent process are outlined below. Throughout, trained BroadReach staff will ensure that women are aware of their right to refuse and/or withdraw from the study at any time. In addition, study staff will emphasize that all study activities are entirely separate from routine HIV care services received and that refusal or withdrawal from the study will have no impact on their ability to access any services provided at any public-sector health facility.

Study procedures

The study will be integrated into Kwamhlanga CHC (rural facility) and Sr Mashiteng Clinic facility (urban facility) in Nkangala district. WLHIV will be recruited directly from the clinic HCT, antenatal care, or ART services. All trained staff are already working in the facility part of the ongoing current APACE (Accelerating Programme Achievements to Control the Epidemic) programme under USAID. The trained study recruiter will recruit eligible directly from women in the study, and if interested and eligible after the screening process, the women will go to a private room for the study consent and interview.

Baseline survey: After consent, a trained interviewer/counselor will administer a brief 10-15 minute survey to n=100 WLHIV about socio-demographics (age, education, relationship status), knowledge of partner's prior HIV testing and status, willingness to distribute HIVSS to their partner(s), facilitators/barriers to HIVSS (17). A trained study staff will ask the survey questions in the local dialect using RedCap. Participants will receive an option to participate in the interview on the phone instead of returning to the health facility.

Randomization: Following the baseline survey, women will be randomized to receive a HIVSS or referral in a 1:1 ratio to the intervention or standard of care arm. Randomization will be performed using a random number table by participant ID, who will be provided with sealed randomization envelopes. The participants will open the envelopes sequentially.

Male partner contact: For women allocated to the intervention arm, the participant will be given a HIVSS to take home to their partner(s). The counsellors will give the participant two options for contacting their partners:

- The participant will contact their partner (via a telephone call or SMS) while in the counselling session to confirm the partner's participation and obtain permission to provide his contact details.
- The participant will ask the partner to contact the counsellor to confirm participation and provide his contact details. If the participant confirms that her partner consented to participate in the study, the counsellor will call him to request his consent over the phone and confirm that he is her partner (using his name and date of birth). The interviewer will read the consent form on the phone and send him a copy via SMS/WhatsApp or email.

Standard of care arm: In the standard of care arm, women will receive standard of care partner referrals for HIV testing, including counselling about disclosure and referral for her partner(s) to return to the facility for testing. They will complete an endline survey after ~3 months (or when they return for their next clinical visit, ART start, or drug pick up visit) to evaluate the uptake of partner testing, results, and safety, including IPV.

Female partner endline survey (intervention arm): Study staff in the facility will conduct a brief 10 minute endline survey in all participants who return at 3 months (or when they return for their next clinical visit, ART start, or drug pick up visit) to report on primary outcomes including partner HIV testing, results and confirmatory testing. If the women do not return in 3 months, UCT staff will conduct the survey telephonically.

Male partner endline survey (intervention arm): Following the survey and counselling, we will ask female participants to ask their partner if he consents (verbally or via SMS/WhatsApp) that we can follow them up. Study staff will contact women who agree in 24-48 hours following the survey to speak with her partner or ask her to give the study phone number to call us to consent to participate in a brief survey. We will attempt to recruit 20 male partners from the intervention arm (n=10 who used the test and n=10 who did not use the test) to provide informed consent to participate in study survey to evaluate use of HIVSS, acceptability (including linking HIVSS to couples testing or disclosure), barriers and any reported harms or reactions over the phone. Male partners will be asked about what they liked about HIVSS, acceptability and ease of use.

Note: All surveys will be translated into isiZulu and back-translated into English to confirm accuracy prior to implementation.

Human Resources: We will train 1-2 BroadReach and DoH HTS counsellors to select the women, consent them and interview them (30-45 minutes) and then either allocate the HIVSS or counselling about importance of partner testing, depending on randomization. A BroadReach Manager will manage the quality of the study and ensure a timely reporting, and contact colleagues at UCT with problems/queries. A trained UCT research staff will conduct the follow up surveys telephonically with women who are unable to return to the facility. The research staff will also conduct interviews with men (n=20) for the endline survey.

Table 1. Pilot study timeline

	Nov	Dec	Jan	Feb	Mar	Apr	May
Mpumalanga Province, District and UCT HREC proposal submission, review and approval	X						
Train HTS counsellors and BR manager in pilot study SOPs, survey and procedures	X						
Develop RedCap survey and pre-test with staff	X						
Recruit and enroll n=100 WLHIV in the study (n=50/month)			X	X			
Baseline survey and eligibility screening (n=100 WLHIV)			X	X			
Randomize n=100 WLHIV to intervention vs standard of care			X	X			
Deliver HIVSS and instructions to n=50 and referral counseling to n=50			X	X			
Follow up participants at ~3 months (to coincide with next clinical visit) to conduct endline survey and evaluate HIV testing uptake, results					X	X	X

(positivity) and linkage (telephonically and using health records)						
Study endline survey for n=20 partners in the intervention arm (telephonically)				X	X	X
Analysis and dissemination					X	X

Evaluation: We will evaluate the following outcomes in the study including:

1. % of index women who self-report that they gave the HIVSS or SOC counseling referral to their male partner
2. % of male partners who either screened or tested for HIV assessed at 3 months after randomization (primary outcome)
 - i. Outcome measured via: index or partner self-report, SMS/WhatsApp of a picture of the used HIVSS sent by partner or index, return of a used self-test to the facility by either the index or partner, and/or partner coming into facility for with an invitation for confirmatory testing or SOC counseling referral
3. % of male partners with a positive HIV screening/test result (case finding)
4. % of newly diagnosed male partners who initiate ART within 3 months of diagnosis
5. % of those on ART with viral suppression after 6 months on ART (index and partners)

4. Ethical considerations

The study protocol, informed consent form, all data collection tools, and other requested documents will be reviewed and approved by the University of Cape Town Faculty of Health Sciences Human Research Ethics Committee (UCT-HREC).

Informed consent

The study informed consent for the study and questionnaire are modelled after that used in previous studies and will be delivered in participants' home language by trained interviewers. The informed consent form (ICF) will be translated into isiZulu and back-translated into English to confirm accuracy. This study ICF details the purpose of the study, study procedures, and the risks and benefits to women that participants may encounter at the second study visit. We will ask women if they want to consent to give her partners' contact information (phone number), but this will not be required to join the study.

Here, study staff will emphasize to participants that:

- Participation is entirely voluntary, and their choice regarding participation will in no way influence the quality of routine medical care for mothers
- Women may exit the study at any time for any reason without compromising the quality of health care received.

Risks

The potential risks to participants in the study include:

- Risks associated with collection of self-reported behavioral and psychosocial information, related to psychosocial distress raised by questionnaire items involving social support, mental health, or disclosure of HIV status
- Risks due to loss of confidentiality due to study procedures—for instance, in the process of data collection
- Risk associated with asking participants to disclose their status, and potential for interpersonal violence by the partner resultant from the disclosure

All participants will be informed of these risks, and the strategies to minimize these, as part of the informed consent process. These strategies draw directly from prior experiences conducting research on HIV prevention and treatment in Mpumalanga.

Safeguards for adverse events: We will screen for IPV risk at baseline and inform women that they do not have to participate in the study if they feel that they are at risk of any violence or harm at home from their partner or anyone else at home. This is in line with prior studies of HIVSS in Malawi and Kenya. Referrals for support related to reported IPV will be given to local social services and NGOs who work with victims of IPV.

5. Benefits

Direct benefit: The primary direct benefit from participating in this pilot study is that women in the intervention arm will receive HIV self-tests for their partner and follow up counseling and support. The proposed intervention is designed to promote case finding, ART linkage and retention in couples living with HIV. We will refer women experiencing IPV to local organizations for counselling and support.

Indirect benefit: By identifying the optimal strategy for improving case finding and index partner testing, this study has the potential to lead to improved HIV treatment interventions to improve case finding interventions across South Africa. Further, if the pilot works and is implemented more widely, it will improve disclosure, ART linkage and potentially retention and viral suppression.

Confidentiality: The following steps will be taken to minimize the risk of any loss of confidentiality throughout study design and conduct.

- All personnel involved in data collection and management will undergo specific training for the study in confidentiality and related patient protection issues.
- Following standard practice, all patient- and study-related information will be kept in locked cabinets at either the BR office.
- Anonymous participant identification numbers will be used on all study documents. Collection of participant names and other identifiers will be restricted to informed consent documents, patient tracing materials, and a study identification key, all of which will be kept in a locked cabinet in the BR office separate from other study documentation and accessible only by the project coordinator and PI. No CRF will include participant name, including CRF that may reflect HIV status of women or their children.
- All electronic records will be kept in password-protected files. All electronic communications of study data will be through password-protected, encrypted files. All data storage at the University of Cape Town will be within a firewall-protected server.

While efforts will be made to minimize the loss of confidentiality, in the event that staff learn that the participant is a threat to themselves or to others or of possible abuse by partners, the proper authorities will be notified. This exception will be included in all study informed consent forms.

References

1. Council HSR. Incidence, Behaviour and Communication Survey, "South African National Prevalence, Incidence, Behaviour and Communication Survey". <http://wwwwhsrcacza/en/media-briefs/hiv-aids-stis-and-tb/sabssm-launch-2018v2>. 2018.

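### The primary outcome accepts any of several sources that differ by arm, so the arm difference mixes partner testing with capture of testing; a like-for-like comparison should stand beside it

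*Combined protocol and SAP*

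**What the plan says.** Aim 2b under Study Objectives makes partner screening or testing at 3 months the primary outcome. It is "Measured via options of: index or partner self-report, SMS/WhatsApp of a picture of the used HIVSS sent by partner or index", and the list continues with return of a used kit and, joined by and/or, the partner's attendance at the facility with an invitation or a referral. Outcome 2 under Evaluation repeats the list: "Outcome measured via: index or partner self-report, SMS/WhatsApp of a picture of the used HIVSS sent by partner or index". The wording implies that any one source is enough. Neither place ranks the sources or says what happens when they disagree.

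The study procedures decide which sources can arise in which arm:

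- **Kits.** Under Male partner contact, in the intervention arm "the participant will be given a HIVSS to take home to their partner(s". The SOC arm receives counselling and a referral of the partner to the facility.
- **Partner contact.** In the same intervention-arm paragraph, "the counsellor will call him to request his consent over the phone and confirm that he is her partner". The male endline survey seeks 20 men, all from the intervention arm. The Informed consent section asks women for partners' phone numbers without limiting this to one arm, but no contact with SOC partners is described.
- **Woman's endline survey.** Planned at about 3 months in both arms, and it asks about partner testing in both.
- **Health records.** The follow-up row of Table 1 refers to "positivity) and linkage (telephonically and using health records". Records are not in the outcome's own source list.

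The Study Objectives section ends by stating the use of the results: "This study will inform a larger trial".

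**The concern.** When one arm has more ways, or different ways, of revealing a test, the observed rates can differ even if the same share of partners tested.

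Sources pull in both directions. Photos, returned kits and partner contact give extra chances to detect a test in the intervention arm. Facility attendance pulls the other way: an SOC partner who follows the referral is seen because he tests at the facility, while a man who screens negative at home has little reason to attend. The background makes the second point more plausible: "HIVSS is a particularly promising strategy to engage African men who are less likely to attend clinic services".

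At stake is the estimate carried forward. An artefact of capture does not shrink with sample size, so a larger trial planned on it could be too small or needlessly large.

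**Working it through.** **No figure to reproduce.** The plan gives 100 women, 50 per arm, with no testing rates, effect size, alpha or power. Every rate below is an assumption.

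**Sources by arm**

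| Source | Intervention | SOC |
|---|---|---|
| Woman's endline report | yes | yes |
| Partner's report | contact and survey described | no contact described |
| Kit photo, returned kit | yes | cannot arise from allocation |
| Facility attendance | confirmatory step | the testing route itself |
| Health records | Table 1, scope unclear | Table 1, scope unclear |

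**Model.** Let pI and pS be true testing, s the share of tests captured by the woman's report, k the share of unreported tests recovered by kit evidence (intervention only), and aI and aS the shares of unreported tests recovered by attendance or records. Sources are taken as independent; overlap of kit evidence with the woman's report is represented by a low k.

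- Observed intervention rate: pI[1 - (1-s)(1-aI)(1-k)]
- Observed SOC rate: pS[1 - (1-s)(1-aS)]
- With pI = pS = 0.5, bias = 0.5(1-s)[(1-aS) - (1-aI)(1-k)]

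**Spurious difference at equal true testing of 50% (points)**

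| aI, aS | k | s = 0.9 | s = 0.7 |
|---|---|---|---|
| 0, 0 | 0.5 | +2.5 | +7.5 |
| 0, 0 | 0.1 | +0.5 | +1.5 |
| 0.3, 0.3 | 0.5 | +1.75 | +5.25 |
| 0.3, 0.3 | 0.1 | +0.35 | +1.05 |
| 0.1, 0.6 | 0.3 | -1.15 | -3.45 |
| 0.1, 0.6 | 0.1 | -2.05 | -6.15 |

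Upper extreme: 0.5 × 0.3 × (1 - 0.5) = 0.075. Lower extreme: 0.5 × 0.3 × (0.4 - 0.9 × 0.9) = 0.15 × (-0.41) = -0.0615.

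**Where the sign changes.** The bias is zero at aS = 1 - (1-aI)(1-k). With aI = 0.1 this is 0.19, 0.37 and 0.55 for k = 0.1, 0.3 and 0.5. The documents cannot place aS on either side of these values.

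**Against the pilot's precision.** 95% CI half-width with 50 per arm and rates near 50%: 1.96 × √(2 × 0.25/50) = 0.196, about 20 points.

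**Carried into a larger trial.** Assume true testing of 70% against 50%, two-sided 5%, 80% power, no dropout, and n per arm = [1.96√(2p̄(1-p̄)) + 0.84√(p1(1-p1) + p2(1-p2))]²/(p1-p2)². Complete capture gives 93 per arm.

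| Basis for planning | s | Apparent difference (points) | n per arm |
|---|---|---|---|
| Any source, k = 0.1 to 0.5 | 0.9 | 16.3 to 21.5 | 144 to 83 |
| Any source, k = 0.1 to 0.5 | 0.7 | 9.0 to 24.5 | 484 to 64 |
| Woman's report, equal capture | 0.9 | 18 | 120 |
| Woman's report, equal capture | 0.7 | 14 | 194 |

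The any-source ends use k = 0.1, aI = 0.1, aS = 0.6 (low) and k = 0.5, aI = aS = 0 (high). At s = 0.7 the low end is 0.7(1 - 0.3 × 0.81) - 0.5(1 - 0.3 × 0.4) = 0.5299 - 0.44 = 0.0899.

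**The same test on the woman's report.** If 10 points more of the 50% of untested SOC partners are wrongly claimed as tested, the SOC rate rises by 0.10 × 0.50 = 5 points. The apparent difference falls to 9 to 13 points, or 478 to 228 per arm. The narrow 14 to 18 range therefore holds only under equal capture and no differential over-claiming.

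**The case against.** **It is a small pilot and the size is assumed.** This stands. If the woman's report is good (90% capture), the bias is at most about 2.5 points, roughly one partner in 50. The wide range needs her report to miss 30% of tests.

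**Accepting the most complete set of sources is legitimate.** This stands too. The background names validation of HIVSS use as a gap, and photos, kits and attendance are more verifiable than an unblinded report. At 90% capture the any-source difference brackets the assumed true 20 points, while the woman's report shows 18. A reader might infer that the woman's report must replace the primary outcome. The documents do not show this, because her report is itself open to under-reporting and to over-claiming that differs by arm.

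**A reader might infer that the outcome favours HIVSS** because more channels sit in that arm. Counting channels does not settle the sign, since attendance captures SOC tests more directly. The opposite inference is no safer. The negative extreme needs attendance or records to recover 60% of unreported SOC tests, the parenthesis on health records in Table 1 may apply to linkage only, and no route to SOC partners' records is described.

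**A reader might infer that SOC women get no telephone follow-up**, because that sentence appears only in the intervention-arm endline paragraph. Human Resources and Table 1 provide telephone follow-up without limiting it by arm, and the Baseline survey paragraph adds: "Participants will receive an option to participate in the interview on the phone instead of returning to the health facility". This is a drafting gap, not evidence of unequal follow-up.

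What survives is that the sources differ by arm and that the plan has no common-source analysis, no tabulation by source and no rule for discordance.

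**Conclusion.** The concern holds in a limited form. As written, the plan compares arms whose tests are ascertained through different sources, so the difference cannot be read as testing alone. Under the assumed inputs the distortion stays well inside the pilot's own uncertainty and would rarely change its conclusion. Its direction is unknown, and its size depends mainly on how completely women report partner testing. The weight of the point lies in using the estimate to plan the larger trial. The asymmetry itself rests on the documents; every magnitude rests on assumed rates and on independence between sources. It is worth correcting because the correction costs little.

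**What to change.** 1. **Add a pre-specified like-for-like comparison** on the index woman's 3-month endline report. Use the same questions, window, contact attempts and telephone back-up in both arms. Count one partner per woman, named before randomisation, since the text allows for several. Take all randomised women as denominator, and handle missing endlines identically in both arms (for example as not known to have tested, with a complete-case version beside it). Report it next to the any-source result and use it when planning the larger trial. Making it primary is open to the team, as a trade-off.
2. **Tabulate the outcome by source and arm**, with agreement between the woman's report and photos, returned kits, partner report and attendance. State one rule for discordant sources. Say whether health records serve testing uptake or linkage only.
3. **Carry the telephone back-up sentence into the Standard of care arm paragraph**, consistent with Human Resources.

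Cost: protocol wording, a little more analysis and possibly some 10-minute calls to SOC women. The added comparison has its own weakness. It can be attenuated (a true 20 points shows as 0.7 × 20 = 14 to 0.9 × 20 = 18) and can be shifted by about 5 points if over-claiming differs by 10 points between arms. That is why the source-by-arm table belongs beside it.

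### Outcome 2d and the partner part of 2e are compared between arms among men selected by post-randomisation testing; no outcome counts ART starts over all randomised women, and Table 1 is too short for partner 2e

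*Combined protocol and SAP*

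**What the plan says.** In the combined protocol and SAP, Study Objectives, Aim 2 introduces outcomes a to e with a stem describing a 1:1 randomised trial "in n=100 HIV+ women to assess, comparing standard of care to intervention arm". Outcome 2b, the primary, is partner screening or testing at 3 months after randomisation. Outcome 2d is the percentage "of newly diagnosed male partners who initiate ART within 3 months of diagnosis". Outcome 2e is the percentage "of those on ART with viral suppression after 6 months on ART (index and partners"). The Evaluation list repeats the five outcomes without naming arms. Its third item is the percentage "of male partners with a positive HIV screening/test result (case finding").

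Women are the randomised unit, 50 per arm (Study design; Randomization). Inclusion criterion 4 requires a partner who is HIV-negative or of unknown status.

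On timing, the standard of care text sets an "endline survey after ~3 months (or when they return for their next clinical visit, ART start, or drug pick up visit"); the intervention text is similar. In Table 1 the row "Recruit and enroll n=100 WLHIV in the study (n=50/month") is marked January and February. The row "Follow up participants at ~3 months (to coincide with next clinical visit) to conduct endline survey" also covers linkage from health records, is not limited to one arm, and is marked to May, the last column.

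**The concern.** A partner enters the 2d denominator only if he tests and is diagnosed after randomisation, and the partner part of 2e only if he then starts ART. HIVSS is intended to change that first step. The men counted in the two arms may therefore be different kinds of men, and a difference in 2d can reflect who was diagnosed rather than what HIVSS did for anyone.

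The background names partner ART uptake as one of three gaps and says HIVSS suits men who are less likely to attend clinics. If the extra men reached through kits link less readily, 2d can rank HIVSS below standard of care while more men per randomised woman start treatment. The results are to inform implementation and a larger trial, so what is at stake is which quantity is carried forward.

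The observation windows for 2d and partner 2e also do not fit the planned follow-up.

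**Working it through.** The plan states no event rates, effect size or sample-size derivation, so there is no figure of its own to reproduce. All rates below are assumptions; 50 per arm and the Table 1 months come from the document.

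**1. Selection alone.** Assume:
- 40% of partners test in either arm and 90% of those diagnosed start ART;
- a further 40% test only because of HIVSS and 50% of those diagnosed start;
- 20% of tested men are positive in both groups;
- HIVSS changes no man's linkage once he is diagnosed.

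Outcome 2d:
- standard of care: 90%;
- HIVSS: (0.40 × 0.90 + 0.40 × 0.50) / (0.40 + 0.40) = 0.56 / 0.80 = 70%.

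ART starts per 100 randomised women:
- standard of care: 100 × 0.20 × 0.40 × 0.90 = 7.2;
- HIVSS: 100 × 0.20 × 0.56 = 11.2.

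So 2d is 20 points against HIVSS while starts are 4.0 per 100 women in its favour.

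**2. Range.** With 30–50% testing in either arm and 25–40% more testing only with HIVSS, 2d under HIVSS is 67–77% against 90%. Starts per 100 women are 7.9–13.0 with HIVSS against 5.4–9.0, and higher with HIVSS in every combination.

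**3. When nothing goes wrong.** If both groups link at 90%, 2d is 90% in each arm. Starts are 7.2 v 100 × 0.20 × 0.80 × 0.90 = 14.4 per 100 women.

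**4. Precision.** In step 1, 50 women per arm give 50 × 0.40 × 0.20 = 4 v 50 × 0.80 × 0.20 = 8 diagnosed men. With 30–50% v 70–80% tested and 10–30% positive, the counts run from about 1.5–7.5 v 3.5–12. Illustrative whole-number results with Newcombe 95% intervals (HIVSS minus standard of care):
- among diagnosed men, 7/11 v 4/5: −16 points (−49 to +31);
- among all randomised women, 7/50 v 4/50: +6 points (−7 to +19).

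Over those testing and positivity rates, with linkage of 80–90% (standard of care) and 60–80% (HIVSS), power for the all-randomised comparison is about 3–31% at two-sided 0.05.

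**5. Table 1 calendar (non-leap year).**
- 1 January to 31 May is 30 + 28 + 31 + 30 + 31 = 150 days. Six months from 1 January is 181 days. Even a partner starting ART on the first possible day falls 31 days short.
- 28 February to 31 May is 31 + 30 + 31 = 92 days, so 3 months after randomisation just fits for the last woman.
- A man diagnosed 1 month after randomisation has a 2d window closing at month 4. An endline at month 3 sees 2 months of it.

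**6. Missing endlines in the proposed measure.** Counting missing as no start, with the step 1 rates and assumed follow-up:
- 90% HIVSS v 70% standard of care: 11.2 × 0.9 − 7.2 × 0.7 = 10.08 − 5.04 = +5.0 points;
- 70% v 90%: 7.84 − 6.48 = +1.4 points;
- no true difference (7.2% in both), 90% v 70%: 6.48 − 5.04 = +1.4 points.

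The true difference in the first two cases is +4.0.

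**The case against.** The background poses its question about men who are newly diagnosed, which is exactly the 2d denominator, and linkage after diagnosis is a legitimate cascade step. The between-arm reading rests on one stem shared by five outcomes in a study of preliminary efficacy; the Evaluation list names no arms. If counts are reported, starts per randomised woman can be approximated from the 2d numerator. All of this stands. It makes 2d worth keeping as description, but it does not make it a randomised comparison, and the Aim 2 stem does present it as one.

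Some stronger readings are tempting and are not supported:
- That 2d must mislead. It does so only if the additional men link differently (step 3), and the documents give no linkage rates.
- That simply assuming lower linkage under HIVSS, say 65% v 90%, shows a 25-point bias. It returns the assumed gap; only the two-group calculation isolates selection.
- That 2b and 2c share the fault. Both are worded over male partners and can be read as covering all of them. For 2c the issue is that a reactive screen and a test result are pooled.
- That confirmation is ignored. Intervention women receive an invitation for confirmatory testing and their endline asks about it. What is missing is a definition of newly diagnosed in 2d.
- That counting missing endlines as no start is safe. Step 6 shows it can shift the estimate either way. The follow-up rates there are assumed, and the plan provides telephone follow-up for women who cannot return.

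**Conclusion.** The concern holds. The 2d and partner 2e denominators form after randomisation through the behaviour the intervention targets, and neither outcome list counts partner ART starts over all randomised women. Under the assumed rates, 2d reads 90% v 70% against HIVSS while starts favour it by 7.2 v 11.2 per 100 women. That size depends wholly on assumed testing, positivity and linkage, and the distortion vanishes if linkage is equal. Index women are not selected in the same way, since they are HIV-positive at entry.

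The timing point needs no assumed rates. Within Table 1 no partner starting ART after randomisation can reach 6 months on ART, and the 2d window can outlast the endline.

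Severity is modest. This is a pilot and either measure will be imprecise; the point is what is estimated and carried forward, not a test result.

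**What to change.** 1. Make the between-arm ART comparison the proportion of all randomised women with at least one partner newly diagnosed and started on ART by 3 months after randomisation, the time point of 2b. Use the ART start date, with the same questions and sources in both arms, and give an estimate with a confidence interval. Show the number without endline data by arm. Give the result both with missing counted as no start and among women with data, and state that neither removes bias if follow-up differs by arm.
2. Keep 2d as a descriptive cascade step with counts and observed time since diagnosis. Count as newly diagnosed only men with a confirmed positive result. In 2c, show reactive screens separately from confirmed positives.
3. Report index women in 2e separately. For partners, either extend the record check beyond Table 1 or drop the outcome.

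The cost is mainly outcome wording and analysis code, since the new count uses largely the 2d data. The questionnaires are not in the supplied text, so check that the standard of care endline asks about confirmation and ART start date. An endline held at an earlier clinic visit will need records to complete the 3 months.

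There are downsides. Men diagnosed late have less time to start ART, and a woman enrolled at the end of February has only about 92 days within Table 1. Partner contact and consent are described under the intervention arm, so record linkage may be less complete under standard of care, and equalising it may need added procedures and ethics review. With 50 per arm the comparison stays imprecise and descriptive.
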